2.2 Analysis sets

A patient is considered to be enrolled into the study if he/or she has signed informed consent. Only a patient who has signed informed consent will be included in the analysis data sets.

In addition, screen failure patients are those who signed the informed consent, but never started the study treatment for any reason. For these patients, the eCRF data collected will not be included in analyses, but will be reported in the CSR as separate listings.

2.2.1 Full analysis set

For the Phase II - Part 1 and Part 3 and for the Japanese safety run-in study, the Full Analysis Set (FAS) comprises all patients who received at least one full or partial dose of assigned combination of study drugs. Patients will be analyzed according to the planned, which is the assigned treatment.

For Part 2 of the study, the FAS comprises all patients randomized to a study treatment, which in this case is treatment dosing schedule. According to the intent to treat (ITT) principle, patients will be analyzed according to the treatment they have been assigned to during the randomization procedure.

Unless otherwise specified, misrandomized patients (misrandomized in the interactive response technology (IRT) system) will be excluded from the full analysis set. Misrandomized patients include patients who are screen-failures, but have been randomized by the investigator before eligibility was finally assessed, however have not been treated. If patients were re-screened and successfully randomized, they will be included in the randomized set according to the dosing schedule treatment assigned in the last randomization.

The FAS will be used for all listings of raw data. Unless otherwise specified, the FAS will be the default analysis set used for all analyses.

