
4.1.4 Japanese safety run-in part

A separate safety run-in part will be conducted in Japan in order to adequately characterize the safety and pharmacokinetic profiles of NIR178 as a single-agent (Figure 4-2). Patients enrolled in this part will be excluded from the primary analysis for efficacy and will also be exempt from the mandatory paired biopsy requirement.

Patients enrolled in the safety run-in part must be hospitalized for the first cycle of therapy for safety monitoring. Patients will receive NIR178 as single agent for the first cycle (28 days). If the patients complete cycle 1 without experiencing DLTs (see Table 6-3), they will initiate combination therapy with PDR001 400mg IV q4weeks starting cycle 2 onwards, and continue at the same dose of NIR178. Patients who experience a DLT in cycle 1 will be permanently discontinued from the study treatment and will not proceed to combination therapy. Patients will continue on combination therapy until they experience unacceptable toxicity, confirmed disease progression per iRECIST or Cheson et al (2014) for DLBCL and/or treatment is discontinued at the discretion of the investigator or the patient.

As of Amendment 6, newly enrolled patients in the Japanese safety run-in will receive NIR178 240mg BID in combination with PDR001 400mg IV Q4W starting Cycle 1 day 1. If the patients complete cycle 1 without experiencing DLTs, they will continue on the same combination therapy of NIR178 and PDR001.

In the CPDR001X1101 study of single agent PDR001 in Japanese patients, the safety and PK of PDR001 for Japanese patients were similar between Japanese and non-Japanese patients and the recommended dose determined for PDR001 in non-Japanese patients was found to be acceptable for Japanese patients. Therefore, the dose for PDR001 in the safety run-in part will be 400 mg IV Q4 weeks.

The period for evaluating DLTs will be cycle 1 (i.e. the first 28 days of treatment with single agent NIR178). **Patients must complete a minimum of 80% of planned therapy during cycle 1 with the minimum safety evaluation and drug exposure or have had a DLT within the first cycle of treatment to be considered evaluable for dose escalation decisions. Dose escalation decisions will occur when the cohort of patients has met these criteria.** Upon comprehensive review of all available safety, PK, and PD data (including that of the

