10.1 Analysis sets

10.1.1 Full Analysis Set

For Part 1, Part 3 and Japanese safety run-in part of the study, the Full Analysis Set (FAS) comprises all patients who received at least one full or partial dose of assigned combination of study drugs. Patients will be analyzed according to the planned treatment.

For Part 2 of the study: the Full Analysis Set (FAS) comprises all patients to whom study treatment has been assigned by randomization. According to the intent to treat principle, patients will be analyzed according to the treatment they have been assigned to during the randomization procedure.

The FAS will be used for all listings of raw data. Unless otherwise specified, the FAS will be the default analysis set used for all analyses.

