2.1.1 General definitions

2.1.1.1 Investigational drug and study treatment

For this study, the investigational drugs are NIR178 and PDR001, each also referred as ‘study drug’. When administered solely, it will be referred as ‘single agent’. The study treatment is defined as NIR178 in combination with PDR001, also termed as ‘combination treatment’. They will be administered in the following dose strengths and forms:

Table 2-11 Dose and treatment schedule

Study treatments	Pharmaceutical form and route of administration	Dose	Frequency and/or Regimen		
			Part 1	Part 2	Part 3
NIR178	40mg, 80mg and/or 160mg capsules for oral use	160mg, 240mg*	Continuous BID	Continuous and intermittent BID per randomization	Continuous or intermittent BID based on Part 1 and Part 2 results
NIR178**	80mg, 240mg Film-coated tablet for oral use	160mg 240mg	Not applicable	Not applicable	Continuous BID
PDR001	100mg powder for solution for infusion	400mg	Every 4 weeks		

*All newly enrolled patients under Amendment 5 will receive NIR178 240mg BID

**As of Protocol Amendment 6, patients enrolled in Part 3 will receive continuous dosing of NIR178 FCT in combination with PDR001

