2.2.2 Safety set

The Safety Set includes all patients from the FAS who have received at least one dose of NIR178 or PDR001. Patients will be classified according to treatment received, where treatment received is defined as:

1. The treatment assigned if it was received at least once, or
2. The first treatment received when starting therapy with study treatment if the assigned treatment was never received.

The safety set will be used for the safety summary of the study.

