2.2.6 Patient Classification

Patients may be excluded from the analysis populations defined above based on the protocol deviations (PD) entered in the database and/or on specific patient classification rules defined in [Table 2-2](#).

Table 2-2 Patient classification based on PDs and non-PD criteria

Analysis set	Protocol deviations leading to exclusion	Non protocol deviation leading to exclusion
Full analysis set	No written informed consent Mis-randomized patients as defined in Section 2.2.1	Patients who did not receive at least one dose of NIR178 or PDR001
Safety set	No written inform consent	Patient who did not receive at least one dose of NIR178 or PDR001 or did not have at least one valid post-baseline safety assessment.
PK Analysis Set	See definition of PK set	Patient who did not have at least one evaluable PK data for NIR178 or PDR001
IG Prevalence Set	No written informed consent	Patient did not have a non-missing baseline IG sample or at least one non-missing post-baseline IG sample
IG Incidence Set	No written informed consent	Patient did not have a non-missing baseline IG sample and at least one non-missing post-baseline IG sample
PK/ECG analysis set	See definition of PK/ECG set	Patient who did not have at least one post-dose matched PK-ECG record

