2.4.1.2 Cumulative dose

Cumulative dose of a study treatment is defined as the total dose given during the study treatment exposure and will be summarized for each of the study treatment components.

The **planned cumulative dose** for a study treatment component refers to the total planned dose as per the protocol up to the last date of study drug administration. The planned cumulative dose is not summarized/listed. It is used for relative dose intensity calculations.

The **actual cumulative dose** refers to the total actual dose administered, over the duration for which the patient is on the study treatment as documented in the treatment page eCRF.

For patients who did not take any drug the cumulative dose is by definition equal to zero.

For continuous dosing, the actual cumulative dose is the sum of the non-zero doses recorded over the dosing period and the planned cumulative dose is the planned starting dose summed over the same dosing period.

For intermittent dosing, the actual cumulative dose should be defined based on the days when the patient is assumed to have taken a non-zero dose during dosing periods. For eg., if a patient's duration of exposure is 31 days with assigned dose (X mg, BID) 2wk-on/2wk-off in 28-days dosing period, then the actual cumulative dose is the total dose administered (includes zero or reduced doses) during the initial 14 days of cycle 1 (ceiling of $31/28 = 1$ complete cycle = 2 wk of dosing) and initial 3 days of cycle 2 ($\min(3,14) = 3$). However, the planned cumulative dose is the planned dose for that patient (constant Y mg) cumulated over the dosing days within the duration of exposure.

As the study treatment is a combination agent, there might be patients in the safety set who did not take one component of study treatment and the cumulative dose for that component would be zero.

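### The SAP gives conflicting rules on whether a patient who received only one study drug belongs to the FAS and the Safety Set

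*SAP*

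**What the plan says.** SAP 2.2.1 sets the rule for Parts 1, 3 and the Japanese run-in: "the Full Analysis Set (FAS) comprises all patients who received at least one full or partial dose of assigned combination of study drugs". Protocol 10.1.1 has the same criterion ("received at least one full or partial dose of assigned combination of study drugs"). SAP 2.2.2 then builds the Safety Set inside the FAS: "The Safety Set includes all patients from the FAS who have received at least one dose of NIR178 or PDR001". Protocol 10.1.2 nests it in the same way. SAP 2.1.1.1 adds: "The study treatment is defined as NIR178 in combination with PDR001".

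Under Protocol 4.1.4, run-in patients at 80 and 160 mg took NIR178 alone for the first 28-day cycle, and PDR001 was added from cycle 2. On a cycle 1 DLT the protocol says: "Patients who experience a DLT in cycle 1 will be permanently discontinued from the study treatment and will not proceed to combination therapy".

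Two other places in the SAP use a looser rule. In Table 2-2 (SAP 2.2.6), the non-deviation reason for exclusion from the FAS is "Patients who did not receive at least one dose of NIR178 or PDR001". SAP 2.4.1.2, on cumulative dose, says that "there might be patients in the safety set who did not take one component of study treatment". The Safety Set row of Table 2-2 also requires a valid post-baseline safety assessment, a condition that SAP 2.2.2 does not contain.

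**The concern.** A Safety Set normally rests on exposure alone: anyone dosed is in. Here it inherits whatever the FAS requires, and the FAS text is tied to the combination. In the single-agent run-in cohorts, the event of interest is the very thing that stops a patient from receiving the second drug. Any loss under the literal reading would therefore be selective: patients with a cycle 1 DLT would be the ones missing, from both numerator and denominator.

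The Safety Set carries all safety output (SAP 2.6.2), including deaths (2.6.2.3), the run-in summaries of DLTs and AEs (2.6.2.6.3) and the individual PK listings (2.6.3). The FAS carries the raw-data listings (2.2.1). The same ambiguity covers any Part 1 or Part 3 patient who received one drug and stopped before the other. Two programmers working from different sections of this SAP could populate the sets differently.

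**Working it through.** No sample size, power or error rate in the documents depends on this point, so there is no plan figure to reproduce. The check is to follow one patient through each rule.

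**Test case:** a run-in patient at 80 or 160 mg takes NIR178 alone, has a cycle 1 DLT and never receives PDR001.

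| Source | Rule, in short | Result |
|---|---|---|
| SAP 2.2.1, Protocol 10.1.1 | Dose of the assigned combination | Out of FAS if read literally; in if a partial dose may mean one component |
| SAP 2.2.2, Protocol 10.1.2 | In FAS, plus a dose of either drug | Follows the FAS result |
| SAP Table 2-2, FAS row | Excluded only if neither drug was received | In FAS |
| SAP 2.4.1.2 | Safety Set may include patients who missed one component | In Safety Set |
| SAP 2.1.1.2 | Study treatment starts at the first non-zero dose of either drug | Patient counts as treated |
| SAP Table 2-2, Safety Set row | Dose of either drug and a valid post-baseline safety assessment | In only if such an assessment exists |

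The literal reading has support in the SAP's own vocabulary. Section 1.1 separates single-agent patients from combination patients, and section 2.1.1.1 defines study treatment as the combination.

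Table 2-2 cannot simply be taken as the governing text either. Its FAS row is not limited by study part, so it would exclude Part 2 patients who were randomized but never dosed, whereas SAP 2.2.1 keeps Part 2 on the intent-to-treat principle.

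**Size under the literal reading (hypothetical counts).** With d DLTs among n dosed patients, a set of all dosed patients gives d/n and the nested set gives 0/(n − d).

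- n = 3, d = 1: 1/3 = 33% becomes 0/2 = 0%.
- n = 6, d = 1: 1/6 = 17% becomes 0/5 = 0%.

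**How readily such a case could arise.** The documents give no DLT rate. For assumed true rates p, the chance of at least one DLT among n patients is 1 − (1 − p)^n.

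| p | n = 3 | n = 6 |
|---|---|---|
| 5% | 14% | 26% |
| 10% | 27% | 47% |
| 20% | 49% | 74% |
| 30% | 66% | 88% |

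**What the record implies.** SAP 1.1 reports six single-agent patients, 3 at 80 mg and 3 at 160 mg, with PDR001 initiated at the beginning of cycle 2. Under Protocol 4.1.4, a DLT at 80 mg would have ended the run-in, 1 of 3 at 160 mg would have brought three more patients, and more than one at 160 mg would have ended it. The run-in was neither expanded nor terminated, and Japanese patients were cleared to join other parts. That implies 0/3 at each level. From Amendment 6, run-in patients are assigned the combination from cycle 1.

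**The case against.** The best defence is that the intention is plain. Table 2-2, SAP 2.4.1.2 and SAP 2.1.1.2 all treat a dose of either drug as enough. SAP 2.2.2 itself refers to either drug and provides for patients who never received their assigned treatment. For Parts 1, 3 and the run-in, that wording would do little if the FAS already demanded both drugs. A partial dose of a combination can fairly be read as one component. In Parts 1 and 3 both drugs start on Cycle 1 Day 1 (Protocol 6.1), so one-drug patients should be uncommon. All of this stands as evidence of intent. It does not settle the matter, because the defining sections do not say it and Table 2-2 has its own conflicts with the text.

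A reader might go further and infer that the SAP removes patients with a DLT from the run-in safety results, or that dose escalation was put at risk. The documents support neither. Removal follows only from one reading of the FAS text, against the other sections. Escalation uses a separate evaluability rule (Protocol 4.1.4, SAP 1.1.4) that expressly counts anyone with a DLT in the first cycle and does not refer to the FAS or Safety Set.

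**Conclusion.** There is a real internal conflict over who belongs to the set behind all safety output. It appears in the defining sections of both documents and is contradicted elsewhere in the SAP. It leaves the inclusion of a one-drug patient undetermined.

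Its practical size in this trial looks small. It concerns CSR tabulation only, and the shift of 17 to 33 percentage points is an illustration, not an effect on observed results. That none of the six single-agent patients is affected is inferred from cohort sizes, the stopping and expansion rules, and the statement that PDR001 began at cycle 2; the documents give no explicit DLT count. For Parts 1 and 3, the number of patients who received one drug only is not stated, so any effect there cannot be sized from the documents. The extra assessment condition in Table 2-2 is a separate discrepancy: it could exclude a dosed patient who left before any later assessment.

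**What to change.** 1. SAP 2.2.2: define the Safety Set without reference to the FAS, as all patients who received at least one dose of NIR178 or PDR001.
2. SAP 2.2.1: for Parts 1, 3 and the run-in, base the FAS on at least one full or partial dose of any study drug. Leave the Part 2 randomized definition unchanged.
3. Table 2-2: delete the post-baseline assessment condition from the Safety Set row, and limit the dosing exclusion in the FAS row to Parts 1, 3 and the run-in so that it matches the text.
4. SAP Section 4: record the departure from Protocol 10.1.1 and 10.1.2, which carry the same wording.

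The cost is a short SAP amendment, or an addendum if the database is already locked (SAP Section 1 provides for both), plus a check of the set flags in the programs. No design or data-collection change is needed. Because the FAS is also the default efficacy set, list any Part 1 or Part 3 patients who received only one drug. Any of them whose best overall response is unknown or not assessed would enter the ORR denominator as non-responders under SAP 2.5.3. Run-in patients are already outside the primary efficacy analysis.

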2.2.2 Safety set

The Safety Set includes all patients from the FAS who have received at least one dose of NIR178 or PDR001. Patients will be classified according to treatment received, where treatment received is defined as:

1. The treatment assigned if it was received at least once, or
2. The first treatment received when starting therapy with study treatment if the assigned treatment was never received.

The safety set will be used for the safety summary of the study.

2.2.3 Pharmacokinetic analysis set

The Pharmacokinetic analysis set (PAS) includes all patients who provide an evaluable PK profile. A profile is considered evaluable if all of the following conditions are satisfied:

- Patient receives one of the planned treatments
- Patient provides at least one PK parameter
- Patient did not vomit within 4 hours after the dosing of NIR178

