2.4.1 Potential for drug interactions

Drug-drug interaction (DDI) between NIR178 and PDR001 are not expected although specific studies have not been conducted.

As an antibody, PDR001 is eliminated through protein catabolism and target-mediated disposition. Therefore, PDR001 is not anticipated to be directly eliminated through hepatic/renal metabolism and excretion or to compete with the elimination of NIR178, which is likely eliminated through metabolism. However, immunomodulatory drugs may induce systemic cytokines that alter CYP-mediated metabolism and affect the clearance of small molecules ([Harvey et al 2014](#), [Girish et al 2011](#)). Therefore, the risk of DDI between PDR001 and the NIR178 cannot be totally excluded. For nivolumab, the Clinical Pharmacology and Biopharmaceutics Review ([Nivolumab FDA application \(2014\)](#)) states that nivolumab did not affect CYP enzyme-related cytokine modulation at doses as high as 10 mg/kg in patients. Nevertheless, concentration measurements of NIR178 in the presence of PDR001 are evaluated in CNIR178X2103J study and will be evaluated in this study to explore a possible pharmacokinetic drug interaction between PDR001 and combined drugs.

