Patients should take NIR178 on an empty stomach (i.e. fast from food and drink, except water) at least 1 hour before or 2 hours after a meal. Each dose may be taken with a glass of water (approximately 8 ounces or approx. 235 mL). An ongoing clinical study (CNIR178X2103J) in NSCLC patients includes an investigation of the impact of food on NIR178 PK. If the results of this study indicate that NIR178 may be taken with or without regard to food, the fasting requirement may be removed and administration instructions will be communicated in writing by Novartis.

Patients should be instructed to swallow whole capsules or tablets and not to chew or open them.

If vomiting occurs during the course of treatment, patients should not take the study drug (NIR178) again before the next scheduled dose.

Patients should be instructed not to make up missed doses. A missed dose is defined as a case when the full dose is not taken within 4 hours after the approximate time of the usual daily dosing. That day's dose should be omitted and the patient should continue treatment with the next scheduled dose.

PDR001

PDR001 will be administered via IV infusion over 30 minutes once every 4 weeks. Infusions of PDR001 can be extended to up to 2 hours if clinically indicated.

Further instructions for the preparation and dispensation of NIR178 and PDR001 are described in the CNIR178X2201 Pharmacy Manual.

Both study drugs will be administered on the same day. The first doses of the combination of NIR178 and PDR001 are administered at Cycle 1 Day 1, which defines the patient's treatment cycles for the study. The start time of PDR001 infusion on dosing days can occur at any given time regardless of the dose administration schedule of NIR178.

All dosages prescribed and dispensed to patients and all dose changes during the study must be recorded on the Dosage Administration Record eCRF.

Dose modifications and reductions should be followed described in [Section 6.2.1](#) and [Section 6.2.2](#).

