10.1.3 Pharmacokinetic analysis set

The Pharmacokinetic analysis set (PAS) includes all patients who provide an evaluable PK profile. A profile is considered evaluable if all of the following conditions are satisfied:

- Subject receives one of the planned treatments
- Subject provides at least one PK parameter
- Subject did not vomit within 4 hours after the dosing of NIR178

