2.6.3 Pharmacokinetic endpoints

Pharmacokinetics of the study drugs will be assessed to support a secondary objective using the PK datasets and will be reported by treatment groups following the general analysis conventions used for the safety set (see [Section 2.1](#)).

PK parameters

PK parameters such as those listed in [Table 2-6](#) will be estimated and reported, when applicable. The PK parameters are derived based on non-compartmental methods for NIR178 and its metabolite NJI765 and PDR001.

Table 2-6 Non-compartmental PK parameters

AUCinf	The AUC from time zero to infinity (ng*hr*mL-1)
AUClast	The AUC from time zero to the last measurable plasma concentration sampling time (tlast) (ng*hr*mL-1)
AUCtau	The AUC calculated to the end of a dosing interval (tau) at steady-state (amount x time x volume-1)
Cmax	The maximum (peak) observed plasma concentration following a single dose administration (ng/mL)
Tmax	The time to reach maximum (peak) plasma concentration following a single dose administration (hr)
T1/2	The elimination half-life associated with the terminal slope (λ_z) of a semi logarithmic concentration-time curve (hr).
¹ CL/F	The total apparent body clearance of drug (L*hr-1)
¹ Vz/F	The apparent volume of distribution during terminal phase (associated with λ_z) (L)

¹ For parent drug only

Descriptive statistics (n, arithmetic mean, CV% mean, standard deviation (SD), median, geometric mean, CV% geo-mean, minimum, and maximum) will be presented by treatment groups using the

PAS for all PK parameters defined in [Table 2-6](#) except Tmax, where only n, median, minimum, and maximum will be presented.

For NJI765, CL/F, Vz/F and elimination half-life will not be reported.

PK parameters estimated for the Japanese patients in Japanese safety run-in study may be reported consolidatively with rest of the Phase II study patients.

All individual PK parameters will be listed by treatment using the safety set.

PK concentrations

Descriptive statistics (n, m (number of non-zero concentrations), arithmetic mean, CV% mean, SD, median, geometric mean, CV% geo-mean, minimum, and maximum) for NIR178, NJI765, and PDR001 concentration will be presented at each scheduled timepoint by treatment using the PAS.

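### The PK analysis set applies the NIR178 vomiting condition to every profile, so vomiting after an oral dose can remove intravenous PDR001 data from the PK summaries

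*SAP*

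**What the plan says.** SAP 2.2.3 admits to the PAS patients with an evaluable PK profile and states: "A profile is considered evaluable if all of the following conditions are satisfied". There are three conditions: a planned treatment was received, one or more PK parameters are available, and "Patient did not vomit within 4 hours after the dosing of NIR178". Protocol 10.1.3 has the same structure and the same last condition: "Subject did not vomit within 4 hours after the dosing of NIR178". No analyte, dose or PK occasion is named in either place.

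SAP 2.6.3 then works with three analytes: "The PK parameters are derived based on non-compartmental methods for NIR178 and its metabolite NJI765 and PDR001". Parameter summaries and mean concentration-time profiles are on the PAS, and descriptive statistics "for NIR178, NJI765, and PDR001 concentration will be presented at each scheduled timepoint by treatment using the PAS". Individual listings and individual concentration-time plots use the safety set.

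SAP Table 2-2 (section 2.2.6) excludes from the PK set a "Patient who did not have at least one evaluable PK data for NIR178 or PDR001".

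**The concern.** The condition makes sense for NIR178 and NJI765, because an oral dose that is vomited may not be absorbed. It has no such basis for PDR001. Protocol 6.1 states "PDR001 will be administered via IV infusion over 30 minutes once every 4 weeks", and Protocol 2.4.1 states "As an antibody, PDR001 is eliminated through protein catabolism and target-mediated disposition". Vomiting a tablet or capsule of another drug removes no PDR001 from the body.

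Serum PDR001 concentrations and PK parameters are a named secondary endpoint (Protocol Table 3-1, SAP Table 1-1). Leaving out sound PDR001 data costs some precision for no gain. It would also make membership of the PDR001 summaries depend on gastrointestinal tolerance of the other drug. In addition, the definition leaves room for two programmers to build different sets from the same data.

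**Working it through.** No design figure is involved, so the check is to trace the rule through the documents.

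**1. Does the condition reach PDR001?** SAP 2.2.3 speaks of a profile in general and requires all conditions together. SAP 2.6.3 derives PDR001 parameters and summarises them on the PAS. So it does.

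**2. Do the events overlap in time?** Protocol 7.2.3 asks sites to record the clock time of vomiting within 4 hours of NIR178 on days with PK samples both before and after the dose. Under continuous dosing those are Cycle 1 Days 1 and 28 (Protocol Table 7-9). For patients starting the combination in Cycle 1, Day 1 is also the first PDR001 infusion, which opens the most densely sampled PDR001 profile: pre-dose, 1 hour after the infusion, Days 8, 15 and 22, then pre-dose in Cycle 2 (Protocol Table 7-8). The early Japanese run-in patients took NIR178 alone in Cycle 1 and began PDR001 in Cycle 2. If the condition is applied to the patient as a whole, vomiting in Cycle 1 would count against PDR001 data from an infusion not yet given.

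**3. Does anything lift the condition?**
- SAP Table 2-2 names both drugs but relies on the word evaluable, which SAP 2.2.3 defines for profiles with the vomiting condition included.
- SAP 2.6.3 permits analysts to drop concentration data from some parameters because of vomiting. That can only remove data.
- SAP 2.2.4 states that the immunogenicity sets are specific to a study drug. The PAS carries no such statement.

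**4. Two readings of the set.**

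| Reading | PDR001 | NIR178 |
|---|---|---|
| Vomiting disqualifies the profile, and the patient if no other profile qualifies | Sound profile not evaluable; patient may leave the PAS | Affected profile excluded, as intended |
| One vomiting-free profile admits the patient | Less data lost | Affected profile stays in unless removed at discretion under SAP 2.6.3 |

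Neither reading gives the right result for both drugs.

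**5. Scale.** Protocol 2.3 reports treatment-related vomiting in 10 of 165 Part 1 patients at 160 mg BID: 10/165 = 6.1%. That counts patients at any time on treatment. For a PK-day figure one must assume a per-dose probability p of vomiting within 4 hours and independence between doses. With k relevant doses, the chance of at least one event is 1 − (1 − p)^k. For the two serial PK days, k = 2:
- p = 0.05%: 1 − 0.9995² = 0.1%
- p = 1%: 1 − 0.99² = 2.0%

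The values of p are assumptions; the documents give none.

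**The case against.** The strongest reply is that the PAS is a set of patients, admitted by having an evaluable profile, and most patients have several chances to provide one. PDR001 is sampled again in Cycle 3 and pre-dose up to Cycle 6. Table 2-2 asks only for evaluable data on one drug or the other, so a patient with good PDR001 data might be thought to pass. This stands in part: on that reading fewer PDR001 data are lost, and the text does not settle which reading applies. It does not rescue the definition, because the same reading lets a compromised NIR178 profile into the set.

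It is also fair that the PDR001 PK analysis is descriptive and that the individual data remain visible in safety-set output. That limits the consequence and leaves the scope of the rule unchanged.

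Three stronger inferences are tempting and not supported:
- **That about 6% of PDR001 profiles would be lost.** The 10/165 counts patients, not profiles. It is not restricted to 4 hours after a dose or to PK days, and it omits unrelated vomiting. It is neither an estimate nor an upper bound.
- **That any NIR178 dose during a 28-day PDR001 profile counts.** With 28 × 2 = 56 doses, the formula above gives 2.8% at p = 0.05% and 43% at p = 1%. But vomiting times are requested only on NIR178 PK days, so the condition cannot be checked as written for most of those doses.
- **That PDR001 estimates are biased.** Nothing in the documents shows that PDR001 exposure differs in patients who vomit.

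**Conclusion.** The point holds as one of scope. Both documents state a condition that is relevant to oral NIR178 and its metabolite in terms that also cover intravenous PDR001, and no other provision limits it. Vomiting after NIR178 can therefore make a PDR001 profile non-evaluable and can remove the patient from the PAS-based PDR001 statistics and mean profiles.

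The number affected cannot be derived, because the definition names neither the occasion nor the level (profile or patient) at which it operates, and no rate of vomiting within 4 hours of a PK-day dose is given. It is probably small. A reader might infer that PDR001 data are discarded from the report altogether; they are not, since listings and individual plots use the safety set. The response-rate analysis and the sample size are untouched. This is a minor correction, worth making because the change is specific and needs no new data.

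**What to change.** In SAP 2.2.3, define evaluability separately by analyte and PK occasion. Apply the vomiting condition only to NIR178 and NJI765 profiles, and only on the PK day on which the vomiting occurred. For PDR001, require a planned treatment and one or more PDR001 PK parameters. State that PAS-based summaries use, for each analyte, the profiles evaluable for that analyte.

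Reword SAP Table 2-2 to match, and record the departure from Protocol 10.1.3 in SAP Section 4. The SAP introduction already provides for such changes by amendment before database lock or by addendum after it. The cost is a short text change in three places and minor extra programming to carry an evaluability flag per analyte and occasion. No further data collection is needed.
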